5.2 Exclusion Criteria

Patients meeting any of the criteria below are not for this study:

1. History of anaphylaxis.
2. Participation in a prior lebrikizumab clinical study.
3. Treatment with any of the following agents within 4 weeks prior to the Baseline visit:
 - a. Immunosuppressive/immunomodulating drugs (e.g., systemic corticosteroids, cyclosporine, mycophenolate-mofetil, IFN- γ , Janus kinase inhibitors, azathioprine, methotrexate, etc.)
 - b. Phototherapy and photochemotherapy (PUVA) for AD.
4. Treatment with TCS or TCI within 1 week prior to the Baseline visit.
5. Treatment with biologics as follows:
 - a. Treatment with an investigational drug within 8 weeks or within 5 half-lives (if known), whichever is longer, prior to the Baseline visit.
 - b. Dupilimab within 3 months of Baseline visit.
 - c. Cell-depleting biologics, including rituximab, within 6 months prior to the Baseline visit.
 - d. Biologics within 5 half-lives (if known) or 16 weeks prior to Baseline visit, whichever is longer.

6. Use of prescription moisturizers within 7 days of the Baseline visit.
7. Regular use (more than 2 visits per week) of a tanning booth/parlor within 4 weeks of the screening visit.
8. Treatment with a live (attenuated) vaccine within 12 weeks before the Baseline visit.
9. Active chronic or acute infection requiring treatment with systemic antibiotics, antivirals, antiparasitics, antiprotozoals, or antifungals within 2 weeks before the Baseline visit, or superficial skin infections within 1 week before the Baseline visit. NOTE: patients may be rescreened after infection resolves.
10. Known or suspected history of immunosuppression, including history of invasive opportunistic infections (e.g., tuberculosis [TB], histoplasmosis, listeriosis, coccidioidomycosis, pneumocystosis, and aspergillosis) despite infection resolution: or unusually frequent, recurrent, or prolonged infections, per the Investigator's judgment.
11. History of human immunodeficiency virus (HIV) infection or positive HIV serology at screening.
12. Positive with hepatitis B surface antigen (HBsAg), hepatitis B core antibody (HBcAb), or hepatitis C antibody at the screening visit.
13. In the Investigator's opinion, any clinically significant laboratory results from the chemistry, hematology or urinalysis tests obtained at the screening visit.
14. Presence of skin comorbidities that may interfere with study assessments.
15. History of malignancy within 5 years before the screening visit, except completely treated in situ carcinoma of the cervix, completely treated and resolved non-metastatic squamous or basal cell carcinoma of the skin.
16. Severe concomitant illness(es) that in the Investigator's judgment would adversely affect the patient's participation in the study. Any other medical or psychological condition (including relevant laboratory abnormalities at screening) that in the opinion of the Investigator may suggest a new and/or insufficiently understood disease, may present an unreasonable risk to the study patient because of his/her participation in this clinical trial, may make patient's participation unreliable, or may interfere with study assessments. Pregnant or breastfeeding women, or women planning to become pregnant or breastfeed during the study.
17. Women of reproductive potential* who are sexually active and unwilling to use adequate birth control. Adequate birth control is defined as agreement to consistently practice an effective and accepted method of contraception[†] throughout the duration of the study and for 120 days after last dose of study drug.

*The following are considered women who are NOT of reproductive potential: Menopausal women, defined as ≥ 12 consecutive months without menses (if in question, a follicle stimulating hormone level of ≥ 25 mU/mL); Women surgically sterilized (history of hysterectomy, bilateral oophorectomy, or bilateral tubal ligation).

[†]Includes abstinence, oral/implant/injectable/transdermal hormonal contraceptives, intrauterine device, double-barrier contraception (i.e., condom+diaphragm), same sex partner, or a male partner with vasectomy.

6 STUDY DRUG

6.1 Study-Drug Formulation and Presentation

The study drug used in this trial will be lebrikizumab and placebo. Lebrikizumab is a sterile liquid solution containing 125 mg/mL lebrikizumab, CCI

Placebo solution is identical in appearance and content to the active solution with the exception of lebrikizumab. All study drug will be supplied as a sterile pre-filled syringe with a pre-assembled needle safety device.

Each prefilled syringe is intended for a single-dose subcutaneous (SC) administration only.

6.2 Study-Drug Supply and Labeling

All study drug will be supplied as a sterile pre-filled syringe (PFS) with a pre-assembled needle safety device. Each PFS will be packaged in a syringe-box.

Pre-filled syringes will be labeled and will contain the pre-printed medication number (MEDNO), along with study drug storage instructions. The syringe-box label will also contain the corresponding pre-printed MEDNO and use by date, along with study-drug storage instructions. In addition, the syringe-box label will contain a write-in space for the patient number, investigator number and administration date. All labels will state "limited by U.S. law to investigational use".

Syringes and syringe boxes will be packaged in a secondary kit and labeled with a Kit Number. Kit Numbers will be assigned to a patient in the interactive web response system (IWRS) based on the study randomization schema.

6.3 Study-Drug Storage

Study drug is to be stored under refrigerated conditions (2–8°C) and protected from excessive light and heat. Study drug should not be frozen, shaken, or stored at room temperature.

Temperature excursions outside of 2–8°C must be reported to the Sponsor or the designee.

6.4 Study-Drug Unblinding

The Sponsor or designee, the Investigator, study-site personnel, and the patient will be blinded to treatment assignment. The integrity of the clinical study will be maintained by observing the treatment blind. If knowledge of a patient's treatment assignment is required for the patient's clinical care and/or safety, the Investigator will open the Code Breaking Card received with the study-drug kit. The Code-Breaking Card should be stored in a secure, locked location at the site. The Investigator should have access to the Code-Breaking Card at all times (e.g., 24/7). The Investigator should consult with the Sponsor's medical monitor prior to obtaining treatment assignment information. The Investigator must document (in the patient's medical record) the date and time the blind was broken, the names of the personnel involved, and the reason that treatment assignment information was required.

6.5 Study-Drug Accountability

The Investigator must keep an accurate record of the number of cartons received, the study drug dispensed/used, and those returned to the Sponsor or designee. The Sponsor will provide forms to facilitate inventory control. All study-drug accountability forms and treatment logs must be retained in the Investigator's permanent study file, and these records must be available for inspection at any time by the Sponsor, its designees, or by regulatory agencies.

The study monitor will perform drug accountability for all study drug at the site, and will assist in returning all used, unused, and expired study drug, to the Sponsor/designees, or destroy it according to the study site's standard operating procedure, if accepted by the Sponsor.

6.6 Patient Randomization

All patients will be randomized to study treatment using an IWRS. Study randomization will occur across study sites. After written informed consent has been obtained, all patients will receive a six-digit screening number (XXX-XXX = site number-patient number), assigned in EDC (via iMedidata Rave in sequential order), which will be assigned by the site. Sites should assign the patient numbers in the order that they are screened and enter patients in EDC in the same order. Following completion of the screening period, and after all patient eligibility requirements are confirmed on Day 1 (Baseline), the patient's screening number will be entered in the IWRS, and the patient will be assigned a patient study-drug kit. One kit will provide all the study drug for that patient based on the assigned treatment group.

Patients will be randomized 3:3:3:2 to one of the following treatment groups. The dosing schedule by treatment group is shown in [Table 1](#).

Treatment Group 1: Lebrikizumab, 125 mg every 4 weeks

Baseline: Loading dose of 250 mg (two injections of 1 mL of 125 mg/mL drug product and two injections of 1 mL placebo);

Week 2: Four 1-mL injections of placebo

Weeks 4, 8, 12: 125 mg (one 1-mL injection of 125 mg/mL drug product and one 1-mL injection of placebo)

Week 6, 10, 14: Two 1-mL injections of placebo

Treatment Group 2: Lebrikizumab, 250 mg every 4 weeks

Baseline: Loading dose of 500 mg (four 1-mL injections of 125 mg/mL drug product)

Week 2: Four 1-mL injections of placebo

Weeks 4, 8, 12: 250 mg (two 1-mL injections of 125 mg/mL drug product);

Week 6, 10, 14: Two 1-mL injections of placebo

Treatment Group 3: Lebrikizumab, 250 mg every 2 weeks

Baseline and Week 2: Loading dose of 500 mg (four 1-mL injections of 125 mg/mL drug product)

Week 4, 6, 8, 10, 12, 14: 250 mg (two 1-mL injections of 125 mg/mL drug product)

Treatment Group 4: Placebo every 2 weeks

Baseline and Week 2: Placebo (four 1-mL injections of placebo)

Week 4, 6, 8, 10, 12, 14: Two 1-mL injections of placebo

Table 1 Dosing Schedule by Treatment Group

Group	Baseline	Week 2	Week 4	Week 6	Week 8	Week 10	Week 12	Week 14
1	250 mg	Placebo	125 mg	Placebo	125 mg	Placebo	125 mg	Placebo
2	500 mg	Placebo	250 mg	Placebo	250 mg	Placebo	250 mg	Placebo
3	500 mg	500 mg	250 mg	250 mg	250 mg	250 mg	250 mg	250 mg
4	Placebo	Placebo	Placebo	Placebo	Placebo	Placebo	Placebo	Placebo

6.7 Study-Drug Administration

Study drug is to be administered to all patients in the clinic by designated and trained study personnel. Study drug should be prepared in advance and injected subcutaneously according to the following instructions:

- Remove study drug from refrigerated condition and allow to warm to room temperature for 15 minutes prior to administration. Study drug should be administered within 4 hours.
- Identify location for injections. Study drug may be injected in the abdomen, upper arm, or thigh. All injections administered at a single visit should be given in the same area, but may be split up into different areas for Week 0 and Week 2, which have 4 injections/visit. Injection sites should be ≥ 10 cm from one another. If possible, injections should not be administered at sites with active AD or other skin lesions.
- Inject study drug subcutaneously.
- Record location of study injections in the eCRF.
- Properly dispose of used syringe according to site requirements. Syringe box must be kept for full drug accountability.

6.8 Concomitant Medications and Procedures

All medications (including over-the-counter drugs, vitamins, and antacids) and over-the-counter emollient(s) taken/used at screening and throughout the study must be recorded.

The sponsor will provide the patient with an over-the-counter emollient. The patient may continue her/his current over-the-counter emollient regimen, if approved by the Investigator.

All medications and treatments taken for AD prior to screening will be recorded separately on an AD medication-history eCRF.

Patients should be instructed to consult with the Investigator prior to initiating any new medication (either self-administered non-prescription drugs or prescription therapy prescribed by another physician) while participating in the study. The Investigator is expected to examine the acceptability of all concomitant medications, topical preparations, and dietary supplements taken by patients participating in the trial.

- Medication entries should be specific to product name (if a combination drug product) and spelled correctly.
- The brand and specific product name for any over-the-counter emollient(s) should be noted and spelled correctly.
- Information on the dose, unit, frequency, route of administration, start date, discontinuation date, indication, and reason for use will be recorded.

- The use of any concomitant medication must relate to an AE listed on the AE eCRF or the patient's medical history unless it is a supplement or used as preventative care.

6.9 Permitted and Prohibited Treatments and Procedures

The use of concomitant medications for other medical conditions (e.g., hypertension, diabetes, acute infections) is permitted during this study. Inhaled corticosteroids to control asthma are permitted.

The introduction of medications or therapies for other medical conditions known to affect AD (e.g., systemic corticosteroids, mycophenolate-mofetil, IFN- γ , Janus kinase inhibitors, TCS (except when given for rescue therapy), TCI, cyclosporine, azathioprine, methotrexate, phototherapy, or photochemotherapy) are not permitted during the study and during the interval prior to entry into the study as defined in the exclusion criteria. In addition, the use of a tanning booth/parlor is not permitted during the trial.

Planned or anticipated major medication procedures or surgeries should be avoided during the trial.

6.10 Rescue Therapy

Patients requiring rescue therapy should consider the addition of TCS prior to considering systemic treatment. Any patient who requires TCS treatment may stay in the study and should continue the TCS for as brief a period as possible. Any patient requiring systemic therapy to treat their AD during the study will be discontinued from the study and the end of study visit assessment should be completed per [Schedule of Visits and Procedures](#). TCS use must be recorded on the concomitant medications eCRF, indicated as "AD therapy".

7 STUDY PROCEDURES

The required procedures for each study visit are outlined in the study [Schedule of Visits and Procedures](#). The timing of each study day is relative to the day of initial dosing (Day 1, Baseline).

7.1 Screening Visit

The purpose of the screening visit/period is to ensure that appropriate patients are entered into the study and that they remain stable during the pre-treatment period.

- Obtain written informed consent prior to performing any study procedures.
- Review Inclusion/Exclusion Criteria.
- Collect demographic information.
- Complete medical history/review of systems.
- Collect concomitant-medication and procedure/therapy information.
- Perform a complete physical examination, including height and weight.
- Measure vital signs.
- Draw blood samples for laboratory tests, including serum pregnancy test (screening visit only).
- Collect urine sample for urinalysis.
- Complete the following assessments:

- Investigator’s Global Assessment (IGA)
- Eczema Area and Severity Index (EASI)
- Body Surface Area (BSA)
- Instruct the patient to apply an emollient twice daily.
- Schedule next visit.

7.2 Baseline Visit (Day 1)

- Confirm emollient use.
- Re-assess and confirm patient eligibility (Inclusion/Exclusion criteria).
- Measure weight and vital signs.
- Collect concomitant medication and procedure/therapy information.
- Query for adverse events (AEs) since the last visit.
- Collect a 12-lead ECG.
- Draw blood samples for laboratory tests (hematology and chemistry)
- Draw a pre-dose blood sample for PK and anti-drug antibody (ADA) testing.
- Conduct urine for urinalysis and urine pregnancy test (WOCBP only).
- Dispense electronic tablet that will be used for home recording of pruritus NRS and sleep-loss NRS (daily), and ADIQ (weekly).
- Train patient on the use of the electronic tablet.
- Review compliance report on the electronic tablet for the assessments (pruritus NRS, sleep-loss NRS, and ADIQ) and remind patient to record daily.
- Complete the following assessments:
 - Investigator’s Global Assessment (IGA)
 - Eczema Area and Severity Index (EASI)
 - Body Surface Area (BSA)
 - Patient Oriented Eczema Measure (POEM)
 - Dermatology Life Quality Index (DLQI)
 - Hospital Anxiety and Depression Scale (HADS).
- Randomize the patient.
- Administer study drug.
- Instruct the patient to apply an emollient twice daily.
- Schedule next visit.

7.3 Visits on Day 15, Day 29, Day 43, Day 57, Day 71, Day 85 and Day 99 (+/- 3 Day)

- Confirm emollient use.

- Measure vital signs.
- Collect concomitant-medication information.
- Review and record AEs.
- Review compliance report on the electronic tablet for the daily assessments (pruritus NRS, sleep-loss NRS, and ADIQ) and remind patient to continue daily record.
- At **Day 29, 57, and 85**, draw blood samples for laboratory tests, and collect urine for urinalysis and pregnancy test (WOCBP only).
- At **Day 29, 57, and 85**, complete the following assessments:
 - Investigator’s Global Assessment (IGA)
 - Eczema Area and Severity Index (EASI)
 - Body Surface Area (BSA)
- At **Day 57** complete the following assessments:
 - Dermatology Life-Quality Index (DLQI)
 - Hospital Anxiety and Depression Scale (HADS).
- At **Day 15, 29, 57, and 85**, collect blood samples for PK (see Section 8.2.2 for instructions).
- At **Day 15 and 29**, collect a pre-dose blood sample for ADA testing (see Section 8.2.2 for instructions).
- Administer study drug.
- Remind the patient to apply an emollient twice daily.
- Remind the patient to use the tablet daily.
- Schedule next visit.

7.4 Visit Day 113 (Week 16) (+/- 3 Day) (End-of-Treatment/Early-Termination Visit)

Patients who discontinue the study early for any reason should have these assessments performed at their early-termination visit. The reason for early termination must be recorded in the patient’s records and the eCRF.

- Confirm emollient use.
- Perform a complete physical examination, including weight.
- Measure vital signs.
- Collect concomitant medication and procedure/therapy information.
- Review and record AEs.
- Collect a 12-lead ECG.
- Draw blood samples for laboratory tests (hematology and chemistry).
- Draw a blood sample for PK and ADA testing.
- Collect urine for urinalysis and urine pregnancy test (WOCBP only).

- Review compliance report on the electronic tablet for the daily assessments (pruritus NRS, including a global impression of change for itching; sleep-loss NRS; and ADIQ).
- Collect electronic tablets and download any remaining data on device.
- Complete the following assessments:
 - Investigator’s Global Assessment (IGA)
 - Eczema Area and Severity Index (EASI)
 - Body Surface Area (BSA)
 - Patient-Oriented Eczema Measure (POEM)
 - Dermatology Life Quality Index (DLQI)
 - Hospital Anxiety and Depression Scale (HADS)
 - Global Assessment of Change for AD.
- Remind the patient to apply an emollient twice daily.
- Schedule next visit.

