Study Objectives:	
 To evaluate the safety and efficacy of lebrikizumab compared with placebo in patients with moderate-to-severe AD. To evaluate the dose-response of lebrikizumab in patients with moderate-to-severe AD.
Duration of Patient Participation:	
 Screening: Maximum duration of 30 days; Treatment period: Approximately 113 days Post-treatment follow-up period: Approximately 111 days Maximum total participation: Approximately 257 days
Study Treatment:	
Lebrikizumab, 125 mg/mL injectable delivered in a pre-filled syringe (PFS)
 
Placebo, 0 mg/mL injectable delivered in a PFS

Study Design:	
This is a randomized, double-blind, placebo-controlled, parallel-group study. Approximately 275 patients with moderate-to-severe AD will be enrolled into this 32-week study.
 
Patients will be seen every two weeks and receive all study drug injections in the clinic. Patients will be evaluated for safety and efficacy through Week 16 on study. A safety follow-up visit will occur at Week 24 and a follow-up phone call will occur at Week 32.
 
Serum PK and anti-drug antibody (ADA) will be collected from all patients. PK samples will be collected at Baseline, Weeks 2, 4, 8, 12, 16, and 24. ADA samples will be collected at Baseline, Weeks 2, 4, 16, and 24.
 
Patients will be randomized 3:3:3:2 to the following treatment groups.
 
Treatment Group 1: Lebrikizumab, 125 mg every 4 weeks
 
Baseline: Loading dose of 250 mg (2 injections of 1 mL of 125 mg/mL drug product and 2 injections of 1-mL placebo)
 
Week 2: Four 1-mL injections of placebo

Weeks 4, 8, 12: 125 mg (one 1-mL injection of 125 mg/mL drug product and one 1-mL injection of placebo)

Weeks 6, 10, 14: Two 1-mL injections of placebo

Treatment Group 2: Lebrikizumab, 250 mg every 4 weeks

Baseline: Loading dose of 500 mg (four 1-mL injections of 125 mg/mL drug product)

Week 2: Four 1-mL injections of placebo

Weeks 4, 8, 12: 250 mg (two 1-mL injections of 125 mg/mL drug product)

Weeks 6, 10, 14: Two 1-mL injections of placebo

Treatment Group 3: Lebrikizumab, 250 mg every 2 weeks

Baseline and Week 2: Loading dose of 500 mg (four 1-mL injections of 125 mg/mL drug product)

Week 4, 6, 8, 10, 12, 14: 250 mg (two 1-mL injections of 125 mg/mL drug product)

Treatment Group 4: Placebo every 2 weeks

Baseline and Week 2: Four 1-mL injections of placebo

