10.2 Early Termination of Study Patients

The Investigator will make every reasonable effort to keep each patient in the study. However, patients may terminate or be terminated early from the study for the following reasons:

- Voluntarily withdrawal of consent to participate in the study participation, at any time
- Adverse event, laboratory abnormality or inter-current illness which, in the opinion of the Investigator, indicates that continued treatment and/or participation in the study is not in the best interest of the patient
- Serious protocol violation, persistent non-compliance or requirement for medication or procedure prohibited by the protocol
- Lost to follow-up

Patients who are terminated early from study will have an Early-Termination visit scheduled (Section 7.4) as soon as possible. All information, including the reason for early discontinuation will be recorded in the patient's study records and in the eCRF.

Before a patient can be terminated early due to loss of follow-up, the Investigator must show documented attempts to contact the patient regarding study participation on two separate occasions (telephone contact) followed by a certified letter of contact.

Prior to discontinuing a patient from study participation, the Investigator will discuss his/her intentions with the Sponsor Medical Monitor or designee.

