10.3 Study-Drug Discontinuation

Study drug must be discontinued for patients who experience the following:

- Inter-current illness that would, in the judgment of the Investigator, affect assessments of clinical status to a significant degree
- Treatment related AEs that are clinically significant, deemed persistent, in the judgment of the Investigator
- Unacceptable toxicity
- Pregnancy

Patients who discontinue study drug permanently during study participation must be scheduled for an Early-termination visit (Section 7.4).

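### Patients discontinued from the study early have no scheduled safety contact after the early-termination visit, while completers are followed for adverse events to 126 days after the last dose

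*Protocol*

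**What the plan says.** **Completers.** The last dosing visit is Day 99 (Protocol 7.3; Appendix 1 confirms no dosing at Week 16). Visits follow at Week 16, Week 20 and Week 24, then a phone call at Day 225 whose only listed item is adverse events (7.4 to 7.7). The Synopsis gives "Post-treatment follow-up period: Approximately 111 days".

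**Patients who leave the study.** Section 10.2: "Patients who are terminated early from study will have an Early-Termination visit scheduled (Section 7.4) as soon as possible". Section 6.10: "Any patient requiring systemic therapy to treat their AD during the study will be discontinued from the study", with an end-of-study assessment. Section 10.1 sends patients to the same early-termination visit if the sponsor stops the trial. None of the three names a later contact.

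**Patients who stop study drug.** Section 10.3: "Patients who discontinue study drug permanently during study participation must be scheduled for an Early-termination visit". It does not say whether participation ends.

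**The visit itself.** Section 7.4 serves both Week 16 and early termination: "Patients who discontinue the study early for any reason should have these assessments performed at their early-termination visit". Its checklist ends with "Schedule next visit". The early-termination column of Appendix 1 has no later contact tied to it.

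**What continues.** Known adverse events are followed until they settle (9.1.5). SAEs after a patient's completion or termination are reportable if the investigator judges them drug-related (9.1.6.1). A patient who becomes pregnant during participation comes off study drug, may remain in the study, and is followed past delivery (9.1.8).

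**The concern.** Safety and dose-response are both stated objectives. Adverse events are a listed reason for leaving the study or stopping drug (10.2, 10.3), so some early stoppers will be patients whose later course matters for safety, and they may be watched for the shortest time.

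The analysis does not fully compensate. SAP 6.15.4 summarises the number of subjects with treatment-emergent events, so unobserved follow-up adds no events to those counts. If early stopping differs between arms, so does the unobserved time, and the between-dose safety comparison can be distorted. Malignancy, one of the events of special interest in 9.1.7, could first appear after an early-termination visit.

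**Working it through.** **1. The plan's own figure.** Week 16 to the Week 32 call: 225 − 113 = 112 days, against about 111 in the Synopsis. It reproduces within rounding.

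**2. Observation after the last dose, completers.** 225 − 99 = 126 days. With visit windows: (225 − 7) − (99 + 3) = 116 to (225 + 7) − (99 − 3) = 136 days.

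**3. The routes side by side.**

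| Route | Protocol section | Visit required | Later safety contact |
|---|---|---|---|
| Completes dosing | 7.4 to 7.7 | Week 16 | Weeks 20, 24, 32 |
| Needs systemic therapy for AD | 6.10 | End-of-study assessment | None named |
| Sponsor stops trial | 10.1 | Early termination | None named |
| Leaves study early | 10.2 | Early termination | None named |
| Stops study drug only | 10.3 | Early termination | Not stated |

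**4. Does the last line of the 7.4 checklist settle it?** No. Section 7.4 also lists PK sampling, ADA sampling and the emollient reminder, and Appendix 1 marks none of these in its early-termination column. The shared checklist is therefore not carried over whole to early termination. Section 9.1.6.1 also treats the time after a patient's own termination as outside the SAE collection window.

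**5. Days lost per patient who stops during dosing.** Let t be the days from last dose to the early-termination visit. The documents do not fix t; visits are two weeks apart, so I take 0 to 14.
- Against the completers' 126 days: 126 − 14 = 112 to 126 − 0 = 126, midpoint 119.
- Against a shorter 120-day yardstick (the contraception period in 5.2) with t = 14: 120 − 14 = 106.

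**6. Patient-years lost.** Planned post-dose time: 275 × 126 / 365 = 94.9 patient-years. Loss = 275 × d × days / 365, where d is an assumed proportion stopping during dosing.

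| d | Patients | At 106 days | At 119 days |
|---|---|---|---|
| 10% | 27.5 | 8.0 | 9.0 |
| 20% | 55 | 16.0 | 17.9 |
| 30% | 82.5 | 24.0 | 26.9 |

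The range is roughly 8 to 27 of about 95. A later stop loses less: a patient whose early-termination visit falls on Day 169 misses 225 − 169 = 56 days.

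**7. Pregnancy.** The last scheduled test for completers is Day 169: 169 − 99 = 70 days after the last dose (60 to 80 with windows). Of the 120-day contraception period, 120 − 70 = 50 days have no scheduled check even for completers.

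**8. Exposure adjustment.** Protocol 11.7 plans three sets of adverse-event tables (treatment, follow-up, combined) and rates per 100 patient-years. It states a denominator only for the treatment period. SAP 6.15.4 carries forward neither the rates nor the period tables, although SAP section 8 declares no changes. SAP 6.15.1 computes days of exposure from first to last injection, so that quantity contains no time after the last injection.

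**The case against.** The strongest reply is that no passage calls the early-termination visit the last contact, and the 7.4 checklist tells the site to arrange another visit. For patients who stop drug only, this stands. Section 10.3 lists pregnancy as a reason to stop drug and requires the early-termination visit, while 9.1.8 lets that same patient stay in the study, so further contact can follow. A reader might infer that the early-termination visit ends contact for everyone; the documents do not support that. For patients discontinued from the study the reply is weaker, for the reasons in step 4.

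Other parts of the reply also stand:
- A reader might infer that events after early termination are simply not collected. That is too broad: known events, drug-related SAEs and pregnancies arising during participation are covered.
- A reader might treat 120 days as a defined safety window. The phrase in 5.2, "throughout the duration of the study and for 120 days after last dose of study drug", is a contraception commitment. The comparison with completers does not need it.
- The gap in pregnancy checks is not peculiar to early stoppers.
- Protocol 11.7 does plan exposure-adjusted rates and a separate follow-up table. This is a partial answer, limited by step 8. Even correct person-time would not remove bias if patients leave because of adverse events.
- The patient-years include placebo patients (50 of 275), and patients who withdraw consent or are lost, many of whom no extra call could reach.

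**Conclusion.** For patients discontinued from the study under 6.10, 10.1 or 10.2, the plan schedules no safety contact after the early-termination visit, against 126 days of post-dose adverse-event follow-up for completers. New non-serious events and SAEs judged unrelated then have no scheduled collection. For drug-only stoppers the plan is ambiguous, and 7.4, 9.1.8, 10.3 and Appendix 1 must be reconciled.

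The size, roughly 8 to 27 of about 95 planned post-dose patient-years, rests on three assumptions: 10% to 30% stop, they stop during dosing, and the early-termination visit is their last safety contact.

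A reader might go further and infer that early stoppers are the patients at highest risk, or that harm on active drug or at higher dose will be understated. Both are possible, but the documents give no dropout rate, no split of reasons for stopping and no figures by arm, so neither the direction nor the size of any bias can be stated. This is a worthwhile, inexpensive improvement to safety data and does not bear on the Week 16 efficacy analysis.

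**What to change.** - **Protocol 6.10, 7.4, 10.1 to 10.3 and Appendix 1:** separate end of study drug from end of safety follow-up, and state for each route which contacts follow the early-termination visit.
- **Protocol 7.7:** make the adverse-event call to every dosed patient who stops early and still agrees to contact, at the completers' interval of about 126 days after the last dose. Add a pregnancy-status question for completers and early stoppers alike, since the call now covers adverse events only.
- **Protocol 9.1.6.1:** align the SAE window with the end of safety follow-up, so that an unrelated SAE learned of at the call is recorded.
- **SAP 6.15.4:** report the number of early stoppers reached by arm, and base follow-up-period event rates on actual observation time rather than on days between first and last injection.

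The cost is amendment wording, one call per early stopper and a slightly longer call form. Some patients will not be reached. Treatment and rescue rules are untouched.
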